## **5.5 Withdrawal of individual subjects**

Not applicable.

## **5.6 Replacement of individual subjects after withdrawal**

Not applicable.

## **5.7 Follow-up of subjects withdrawn from treatment**

Not applicable.

## **5.8 Premature termination of the study**

Not applicable.

## **6. SAFETY REPORTING**

### **6.1 Temporary halt for reasons of subject safety**

Not applicable.

### **6.2 Serious adverse events (SAEs)**

Not applicable.

### **6.3 Follow-up of adverse events**

Not applicable.

### **6.4 Data Safety Monitoring Board (DSMB)**

Not applicable.

## 7. STATISTICAL ANALYSIS

Descriptive statistics will be used to describe the study population, and data are expressed in number and relative proportions for categorical variables and median (quartile 25% – quartile 75%) for continuous variables.

As the outcome of this study is urgently needed, data analysis will be done in two sequential steps. The first step includes an analysis of all patients admitted for invasive ventilation in one of the participating ICUs in the first four weeks after admission of the first COVID–19 patients, which was in all centers within the first weeks of March 2020. This part of the analysis focusses on ventilation practices in the first weeks of the pandemic in the Netherlands. This analysis may underestimate the effect of ventilation variables and parameters on outcomes, as many patients will not yet be weaned from the ventilator and remain admitted in the ICU. The second step includes an analysis of all COVID–19 patients admitted during the total 10 weeks PRoVENT COVID will enroll patients, with a complete follow up till day 90. This analysis will provide an answer to the question whether certain ventilator settings, variables and parameters are associated with patient–centered and other important outcomes.

All analyses will be performed using multilevel (patients nested in hospitals), mixed modelling with hospitals as random effect. Ventilatory variables and parameters will be compared among the groups, and absolute differences with the respective 95%–confidence interval (CI) will be calculated as the absolute difference from a mixed–effect linear model considering the hospitals as random effect to account for within–center clustering. Categorical variables will be compared as the risk difference from the same model.

Cumulative distribution plots will be used to demonstrate the cumulative distribution frequency of ventilation variables. Vertical dotted lines will represent the cut–off for each variable and the horizontal dotted lines the respective proportion of patients reaching each cut–off. Cut–offs to form matrices may use widely accepted values for each variable, specifically 8 mL/kg PBW for tidal volume, 10 cm H2O for PEEP, 30 cm H2O for plateau pressure, and 15 cm H2O for ΔP.

Mixed–effect multivariable logistic or linear regression model will be used to identify factors independently associated with major outcomes, like death and VFD–28. Subanalyses are planned to investigate differences in ventilation practice and outcomes in the following prespecified subgroups: women versus men, and patients categorized by the body mass index.

All analyses will be conducted in R v.3.6.0 and a p value < 0.05 will be considered statistically significant.

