## **SUMMARY**

### **Rationale**

The novel coronavirus disease (COVID–19) pandemic is rapidly expanding across the world, with over 60.000 new cases each day as of late March 2020. Healthcare workers are struggling to provide the best care for patients with proven or suspected COVID–19. Approaches for clinical care vary widely between and within countries and new insights are acquired rapidly. This includes the way invasive ventilation is applied.

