#### 5.1.2 Secondary study parameters

- Number of ventilation-free days and alive at day 28 (VFD-28);
- Duration of ventilation in survivors;
- Use of prone positioning;
- Use of recruitment maneuvers;
- Incidence of acute kidney injury (AKI);
- Duration of ICU stay;
- Duration of hospital stay;
- ICU mortality;
- Hospital mortality;
- 28-day mortality; and
- 90-day mortality.

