### 5.4.3 Repeated measures

- Within one hour after initiation of ventilation OR within first hour of arrival when the patient has been intubated in another hospital, AND 3 times a day at fixed time points (8:00 AM, and 4:00 PM and 8:00 PM) for a following 3-day period:
  - Ventilation data
    - Ventilation mode;
    - Tidal volume set ( $V_T$ ) (mL);
    - Expiratory tidal volume (VTE);
    - Positive end-expiratory pressure (PEEP) (cm H2O);

- Maximum airway pressure ( $P_{\max}$ ) (cm H2O) or plateau pressure ( $P_{\text{plateau}}$ ) or peak pressure ( $P_{\text{peak}}$ ) (cm H2O);
  - Level of pressure support above PEEP (cm H2O);
  - Inspired fraction of oxygen ( $\text{FiO}_2$ ) (%);
  - Set measured respiratory rate (RR) (min);
  - Inspiration to expiration ratio (I:E) (ratio);
  - Saturation of peripheral oxygen ( $\text{SpO}_2$ ) (%); and
  - End-tidal carbondioxide ( $\text{ETCO}_2$ ) (kPa).
- Arterial blood gas (ABG) analysis
  - pH;
  - Partial pressure of oxygen ( $\text{PaO}_2$ ) (kPa or mmHg);
  - Partial pressure of carbon dioxide ( $\text{PaCO}_2$ ) (kPa or mm Hg);
  - Bicarbonate ( $\text{HCO}_3^-$ ) (mmol/L);
  - Arterial saturation of oxygen ( $\text{SaO}_2$ ) (%);
  - Arterial lactate levels (mmol/L);
  - $\text{FiO}_2$  (%) at time point of ABG; and
  - Position of patient in which ABG was taken.
- Hemodynamics
  - Mean arterial pressure (mmHg);
  - Heart rate (bpm);
- 3 times a day at fixed time points (8:00 AM, and 4:00 PM and 8:00 PM) for a following 3-day period:
  - Received paralytic drugs within the previous 8 hours (yes or no).
- Every day at 8:00 AM for 72-hour period after admission
  - Life status (alive or deceased);
  - Location (in ICU, hospital or other facility);
  - Intubation status;
  - Sequential Organ Failure Scores (SOFA);
  - Cumulative dose of sedatives (mg);
  - Cumulative dose of vasopressors (mg);
  - Cumulative fluid balance during last 24 hours (ml);
  - Amount of fluid administered during last 24 hours (ml);
  - Urine output (ml/hour); and

- Plasma creatinine (mmol/L).
- Prone position (yes or no), and if yes, time and duration (hours);
- ABG in supine position;
- Use of recruitment maneuver (yes or no);
- Undergoing veno–venous, veno–arterial or arterio–venous extracorporeal membrane oxygenation (ECMO) (yes or no);
- Pneumothorax (yes or no)

- Follow-up
  - Life status at day 7, day 28 and day 90;

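### Do the death and VFD-28 models need to be restricted to Step 2, given that the Step 1 caveat warns only of underestimation?

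*Combined protocol and SAP*

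**What the plan says.** Section 7 splits the analysis in two because results are needed urgently.

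- **Step 1** covers patients ventilated in the first four weeks after the first COVID-19 admissions. Its purpose: "This part of the analysis focusses on ventilation practices in the first weeks of the pandemic in the Netherlands". Its caveat: "This analysis may underestimate the effect of ventilation variables and parameters on outcomes, as many patients will not yet be weaned from the ventilator".
- **Step 2** covers the full ten weeks of enrolment, with follow-up complete to day 90. Its purpose: "This analysis will provide an answer to the question whether certain ventilator settings, variables and parameters are associated with" patient-centred and other outcomes.

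The modelling text comes after both steps and names neither. It opens "All analyses will be performed using multilevel" and sets hospital as a random effect. Later it says that a mixed-effect "multivariable logistic or linear regression model will be used to identify factors independently associated with major outcomes, like death and" VFD-28.

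Section 5.1.2 defines VFD-28 as ventilation-free "days and alive at day 28". Section 5.4.3 collects "Life status at day 7, day 28 and day 90", with extubation date. Section 7 gives no outcome data cut for Step 1 and no rule for patients still ventilated at that cut.

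**The concern.** The Step 1 caveat speaks of an effect of ventilation variables on outcomes, which is odd if Step 1 estimates no such effect. The modelling sentences carry no step label. Read together, they could permit death and VFD-28 models on Step 1 data while many patients are still ventilated. VFD-28 would then be incomplete for some patients, and length of follow-up would depend on admission date.

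Bias in that setting need not be towards the null. It depends on whether unresolved patients are counted as alive or dropped, on whether a setting changes the timing of extubation or death, and on whether settings drift over calendar time. The Summary makes drift plausible ("Approaches for clinical care vary widely between and within countries and new insights are acquired rapidly"). A reader told only of underestimation might take an early association as a lower bound, which it need not be. That matters for a study meant as a first step towards ventilation guidelines.

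**Working it through.** The plan states no power, event rate or Step 1 data cut, so there is no figure of its own to reproduce. The inputs from section 7 are the 28-day Step 1 window and the 28-day horizon of VFD-28. Everything else is an assumption: 400 patients, uniform entry over the window, liberation 0.05/day, death 0.02/day (total 0.07/day).

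**1. How incomplete is Step 1?** With the outcome cut L days after the window closes, the share with 28 days of follow-up is min(1, L/28). The share unresolved because of the cut is [exp(−0.07L) − exp(−1.96)]/1.96.

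| L (days) | 28 days of follow-up | Unresolved because of the cut |
|---|---|---|
| 0 | 0% | (1 − 0.141)/1.96 = 44% |
| 7 | 25% | (0.613 − 0.141)/1.96 = 24% |
| 14 | 50% | (0.375 − 0.141)/1.96 = 12% |
| 28 | 100% | 0% |

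**2. Direction and size without drift.** Simulated limits (1.5 million patients per scenario), cut at L = 0, odds ratio (OR) for death per SD of a setting, log-hazard effects of 0.1 in size:

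| Effect of the setting | Complete follow-up | Unresolved counted alive | Unresolved dropped |
|---|---|---|---|
| Slows liberation, speeds death | 1.19 | 1.16 | 1.22 |
| Slows liberation only | 1.07 | 1.04 | 1.10 |
| Slows both | 0.96 | 0.94 | 1.00 |

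Each row moves towards the null under one rule and away from it under the other.

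**3. Against sampling error.** The standard error (SE) of the log OR per SD is about 1/√(np(1−p)).
- Complete follow-up: p = (2/7)(1 − 0.141) = 0.245, so SE = 1/√(400 × 0.245 × 0.755) = 0.12.
- L = 0, counted alive: p = (2/7)(0.56) = 0.16, so SE = 1/√(400 × 0.16 × 0.84) = 0.14.
- L = 0, dropped: n = 0.56 × 400 = 224 and p = 0.286, so SE = 1/√(224 × 0.286 × 0.714) = 0.15.

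The smallest shift is ln(0.96/0.94) = 0.021 and the largest ln(1.00/0.96) = 0.041. Relative to the SE at the cut these are 0.021/0.14 = 0.15 and 0.041/0.15 = 0.27, so about 0.1 to 0.3 SE.

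A stronger effect gives more. With a binary exposure that cuts extubation from 0.05 to 0.03/day (death 0.015/day, 51% unresolved), the OR of 1.31 becomes 1.18 if unresolved patients count as alive and 1.67 if they are dropped. For the latter, n = 0.49 × 400 = 196 and p is about 0.28, so SE is about 2/√(196 × 0.28 × 0.72) = 0.32. The shift ln(1.67/1.31) = 0.24 is about three quarters of an SE.

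**4. Drift, no true effect.** False-positive rates at the 5% level, death / VFD-28, unresolved scored alive with zero VFD (4,000 datasets per cell, Monte Carlo error about 0.35 points at 5%):

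| Drift over four weeks | L = 0 | L = 7 | L = 14 | L = 28 |
|---|---|---|---|---|
| 0.25 SD | 5.8 / 6.8% | 5.2 / 5.1% | 4.3 / 4.5% | 5.2 / 5.3% |
| 0.5 SD | 7.6 / 11.2% | 5.7 / 6.2% | 5.3 / 5.2% | 5.1 / 5.6% |
| 1 SD | 17.0 / 28.0% | 8.2 / 7.6% | 5.9 / 5.5% | 4.9 / 5.2% |

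With unresolved patients dropped, death stays at 4.5 to 5.5%. VFD-28 at 1 SD gives 8.6, 13.3, 11.1 and 5.2% across the four cuts.

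**5. Is L = 0 realistic?** Section 5.4.3 measures patients over a following three-day period, and section 5.3 has researchers visit centres to collect data. The four-week window also appears to run from each centre's own first admission. Under a common cut, only the last centre to close could then have no lag.

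**The case for a change.** The strongest case for a change is that the caveat serves no purpose unless Step 1 may yield an effect estimate, and that it names one direction when both are possible. A one-sentence restriction would be cheap, and day-28 status and extubation dates are already collected. Two parts of this stand: no sentence makes the restriction explicit, and the caveat is incomplete.

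The rest is weaker. In context, the caveat reads naturally as the reason why the association question waits for Step 2, the step said to answer it. The sentence on all analyses fixes the model form. It cannot set scope literally, since the same section includes medians, quartiles and cumulative distribution plots. VFD-28 is defined at day 28, so fitting it earlier would depart from the plan's own endpoint, and nothing proposes that. The caveat is also hedged, and its stated direction is correct for the first two scenarios in the no-drift table when unresolved patients count as alive. Deleting it would remove the plan's only warning about incomplete Step 1 follow-up.

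**Conclusion.** No change is needed. This is a missing explicit restriction that a competent analyst supplies from the surrounding text: Step 1 describes practice, and Step 2 estimates associations once every patient has passed day 28. On that reading the truncation bias does not arise. The primary objective in section 2.1.1 is descriptive and is untouched.

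If someone did fit the models early, the bias could go either way, but its size is unknown. Under the assumed rates, modest effects and no drift, it is 0.02 to 0.04 in the OR per SD, well inside sampling error. The high false-positive rates (17.0% for death, 28.0% for VFD-28) need a 1 SD drift within four weeks and an outcome cut on the day the window closes. The documents report no such drift, and the data collection arrangements make that cut unlikely. At 0.5 SD and a seven-day lag the rates are 5.7% and 6.2%. The main exception beyond the first week is VFD-28 with unresolved patients dropped under 1 SD drift (13.3% at seven days, 11.1% at fourteen). Anyone reporting a Step 1 outcome association should not present it as a lower bound. That is a matter of careful reporting and does not require a change to the plan.

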### **Objective**

To determine and compare invasive ventilation settings and parameters in COVID–19 patients in the Netherlands, and to determine associations with clinical outcomes.

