### **Hypotheses**

Invasive ventilation settings and parameters vary between intensive care units (ICUs) in hospitals in the Netherlands; certain ventilator settings have an independent association with duration of ventilation in COVID–19 patients.

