## **2. OBJECTIVES AND HYPOTHESIS**

### **2.1 Objectives**

#### **2.1.1 Primary objective**

To determine and compare invasive ventilation settings and parameters in COVID–19 patients in intensive care units (ICU) of hospitals in the Netherlands.

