### **2.2 Hypothesis**

#### **2.2.1 Primary hypothesis**

There is substantial variation in ventilation practices in COVID–19 patients admitted to the ICU's of hospitals in the Netherlands.

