## **4. STUDY POPULATION**

### **4.1 Population (base)**

The data of at least 1,000 consecutively invasively ventilated COVID–19 patients admitted to intensive care units (ICUs) of hospitals in the Netherlands. This study will not be restricted to the ‘formal’ ICUs, as patients may also receive invasive ventilation at other locations within the hospital during the COVID–19 pandemic.

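### Section 7 plans no between-hospital result, so the Summary hypothesis that ventilation settings vary between ICUs is left without a reported answer

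*Combined protocol and SAP*

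**What the plan says.** The primary hypothesis appears in two wordings. In the Summary (Hypotheses) it is that "Invasive ventilation settings and parameters vary between intensive care units (ICUs) in hospitals in the Netherlands". In Section 2.2.1 it is that "There is substantial variation in ventilation practices in COVID–19 patients admitted to the ICU's of hospitals in the Netherlands", which gives neither the level of the variation nor a threshold for substantial.

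The objective also has two wordings: "To determine and compare invasive ventilation settings and parameters in COVID–19 patients in the Netherlands" in the Summary, and "To determine and compare invasive ventilation settings and parameters in COVID–19 patients in intensive care units (ICU) of hospitals in the Netherlands" in Section 2.1.1. Neither says what is compared with what.

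For the settings, Section 7 plans:

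- medians and quartiles;
- multilevel models with patients nested in hospitals, "considering the hospitals as random effect to account for within–center clustering";
- absolute differences and risk differences with the statement that "Ventilatory variables and parameters will be compared among the groups";
- cumulative distribution plots in which the guide lines show "the horizontal dotted lines the respective proportion of patients reaching each cut–off";
- subanalyses by sex and by body mass index.

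The unit shifts as well. The Summary speaks of ICUs, Section 7 models hospitals, and Section 4.1 notes that "patients may also receive invasive ventilation at other locations within the hospital".

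**The concern.** A hypothesis about variation between units needs a result that separates units from patients. Nothing named in Section 7 does so. The descriptive outputs are pooled. The comparison is among groups that are not defined where they are mentioned. The available readings are the sex and BMI subgroups, or groups formed by the tidal volume, PEEP, plateau pressure and driving pressure cut-offs. None of these compares hospitals.

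If the plan is followed exactly, the report will show how widely settings were spread across patients, but not whether that spread reflects differences between hospitals. If the between-hospital result is added later, the choice of setting, time point and measure will be made with the data in hand. There are nine listed main parameters (Section 5.1.1), recorded at baseline and three times a day for three days (Section 5.4.3).

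**Working it through.** **Step 1. Match each hypothesis to a planned output.** The documents give no ICC, SD or number of hospitals, so there is no figure of the plan's own to reproduce.

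| Wording | What would answer it | Planned in Section 7? |
|---|---|---|
| Section 2.2.1, read as spread across patients | Pooled quartiles, cumulative plots, proportions at cut-offs | Yes |
| Summary, variation between ICUs | Between-unit SD, ICC, unit-specific estimates, or a test or display by unit | No. The hospital variance is fitted but is not named as a result |

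**Step 2. Can the pooled display stand in for the missing result?** Assumed inputs: tidal volume normal, mean 6.5 and total SD 1.2 mL/kg PBW, with the total SD held fixed as the ICC varies. The 8 mL/kg cut-off is from Section 7.

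- Pooled proportion above 8: z = (8 − 6.5)/1.2 = 1.25, so 10.6%. It does not depend on the ICC, because the total SD is fixed.
- Between-hospital SD = 1.2 × √ICC. Within-hospital SD = 1.2 × √(1 − ICC). The middle 95% of true hospital means is 6.5 ± 1.96 × between-hospital SD.
- At ICC 0.10: between-hospital SD 0.379, within-hospital SD 1.138, hospital means 5.756 to 7.244. Then z = (8 − 5.756)/1.138 = 1.97 gives 2.4%, and z = (8 − 7.244)/1.138 = 0.66 gives 25.3%.

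| ICC (assumed) | Pooled above 8 mL/kg | 95% range of true hospital proportions |
|---|---|---|
| 0 | 10.6% | 10.6% everywhere |
| 0.05 | 10.6% | 4.2% to 20.2% |
| 0.10 | 10.6% | 2.4% to 25.3% |
| 0.20 | 10.6% | 0.9% to 33.8% |

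One pooled curve fits all four rows. Another mean or SD would change the percentages, but a pooled curve would still not identify the ICC.

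**Step 3. How precise would the missing estimate be?** Take N = 1,000 (the minimum expected in Section 4.4), s equal-sized hospitals (assumed), k = N/s patients each, and one value per patient. With r the ICC, F = (1 + (k − 1)r)/(1 − r). The limits are (F* − 1)/(F* + k − 1), where F* is F divided by the 97.5% F quantile on (s − 1, N − s) degrees of freedom, or F multiplied by that quantile on (N − s, s − 1).

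Example with s = 10 and r = 0.10: k = 100 and F = 10.9/0.9 = 12.11. Lower: F* = 12.11/2.127 = 5.695, and 4.695/104.695 = 0.045. Upper: F* = 12.11 × 3.340 = 40.45, and 39.45/139.45 = 0.283.

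| Hospitals (assumed) | 95% CI at ICC 0.10 | 95% CI at ICC 0.05 |
|---|---|---|
| 10 | 0.045 to 0.283 | 0.019 to 0.166 |
| 20 | 0.052 to 0.207 | 0.021 to 0.119 |
| 40 | 0.057 to 0.174 | 0.021 to 0.102 |

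Unequal hospital sizes would widen these intervals somewhat.

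**Step 4. Would raw proportions by hospital do instead?** A chi-square homogeneity test on the proportions above 8 mL/kg was simulated under the same assumptions (N = 1,000, equal sizes, 20,000 runs). For 10, 20 and 40 hospitals, power is about 92%, 92% and 87% at ICC 0.10, and about 72%, 66% and 51% at ICC 0.05. Type I error is close to 5%. Raw proportions can therefore often detect variation, but the test does not say how large it is.

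**The case against.** The strongest reply is that the mixed models already contain the hospital variance, so only an output is unnamed. It adds that the body of the protocol governs: Sections 2.1.1 and 2.2.1, the main parameters and the stated focus of the first analysis step can all be read as descriptive, and Section 7 serves that reading. The two hypotheses are also compatible with each other.

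Much of this stands. The gap concerns what is reported, and the description is sound. The ICU/hospital mismatch is minor, since ventilation outside formal ICUs makes hospital the sensible level and Section 7 already uses it. What the reply does not do is supply a result for the Summary hypothesis. The only purpose Section 7 gives for the random effect is to allow for clustering.

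A reader might infer two stronger points, and neither is supported. The first is that the planned analysis is incapable of answering the Summary hypothesis. The documents do not support this, because the models specified in Section 7 would yield the hospital variance. The second is that only a variance estimate could settle the question and simple proportions by hospital could not. Nothing in the documents implies that, and Step 4 shows that a homogeneity test would often detect the variation. The SD and ICC are preferred because they quantify it.

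**Conclusion.** The point holds as a cheap improvement. The outputs named in Section 7 do not address the Summary hypothesis of variation between ICUs, although the fitted models would provide the means. It touches only the between-unit part of the primary question, not the patient-level description or the outcome models.

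The textual finding rests on the documents alone. The size of what could go unseen (2.4% to 25.3% across hospitals behind a pooled 10.6%) rests on an assumed normal distribution, mean 6.5, fixed total SD 1.2 and ICC 0.10. The precision figures rest on assumed numbers of equal-sized hospitals.

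**What to change.** 1. For each main setting in Section 5.1.1, at one stated time point (for example the first recorded value), fit a mixed model with a hospital random intercept and no group term.
2. For continuous settings, report the between-hospital SD and ICC with 95% CI. For categorical settings such as ventilation mode, report a corresponding measure, such as a median odds ratio for a binary form or the distribution by hospital.
3. Add a plot of hospital estimates, and name hospital as the unit of comparison.
4. State that unadjusted variation includes case mix as well as practice. Adjustment can be optional, because Section 5.4.2 allows severity to be recorded as APACHE II, APACHE IV or SAPS II.
5. State that the first value in patients transferred under ventilation may reflect the earlier hospital, and repeat the analysis without them. Section 4.3 excludes only those with more than 24 hours in a non-participating hospital, and Section 5.4.2 records transfer status.
6. Align the Summary hypothesis with Section 2.2.1, saying whether variation between hospitals, across patients, or both is meant.
7. Define the groups in Section 7.

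The cost is modest extra analysis and some rewording, with no new data. The drawback is limited precision if hospitals are few: with 1,000 patients at an assumed ICC of 0.10, the interval is about 0.045 to 0.283 with 10 hospitals, against 0.057 to 0.174 with 40.

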### **4.4 Sample size calculation**

No formal sample size calculation is needed. We expect to capture at least 1,000 patients, but will continue collecting data of new patients for at least 8 weeks.

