## 5. METHODS

### 5.1 Study parameters/endpoints

#### 5.1.1 Main study parameters

- Ventilation mode;
- Tidal volume set ( $V_T$ ) (mL);
- Expiratory tidal volume (VTE)
- Positive end-expiratory pressure (PEEP) (cm H2O);
- Maximum airway pressure ( $P_{max}$ ) (cm H2O) or plateau pressure ( $P_{plateau}$ ) or peak pressure ( $P_{peak}$ ) (cm H2O);
- Level of pressure support above PEEP (cm H2O);
- Inspired fraction of oxygen (FiO2) (%);
- Set and measured respiratory rate (RR) (min); and
- Inspiration to expiration ratio (I:E) (ratio).

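### Risk differences for binary variables come from a linear mixed model with one residual variance, so their 95% intervals miss nominal coverage when groups are unequal and uncommon event rates differ

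*Combined protocol and SAP*

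**What the plan says.** The third paragraph of Section 7 compares ventilatory variables among groups by a linear mixed model with a random hospital effect, and promises that "absolute differences with the respective 95%–confidence interval (CI) will be calculated". A later sentence extends this to proportions: "Categorical variables will be compared as the risk difference from the same model". The only model this can refer to is the linear one just described. Section 7 names no binomial family, separate variance per group, robust standard error or rule for sparse events.

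The groups in that paragraph are not defined. The subgroups prespecified later in Section 7 are "women versus men, and patients categorized by the body mass index", with no sizes. A mixed-effect logistic model does appear there, but for factors associated with major outcomes such as death, not for these group comparisons. The threshold is "a p value < 0.05 will be considered statistically significant".

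Section 4.4 says "No formal sample size calculation is needed" and gives an expected size of at least 1,000. Section 5.1.1 lists "Ventilation mode" first among the main study parameters, without its categories.

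**The concern.** A linear mixed model in its standard form estimates one residual variance for all patients. For a yes/no variable the variance follows from the rate, so two groups with different rates have different variances. When the groups are also of different size, the pooled variance is dominated by the larger group, while the sampling error of the difference is driven mainly by the smaller one. The reported standard error is then too small if the smaller group has the higher rate and too large if it has the lower rate. More patients do not help, because at a fixed split both the model variance and the true variance shrink in proportion to 1/N.

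The primary objective is to determine and compare practice across ICUs, and these intervals are how differences in binary variables would be reported. Point estimates of the risk difference are not in question. What is at stake is the precision claimed for real differences in uncommon events, most of all in a small body mass index class.

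**Working it through.** **Inputs from the documents.** At least 1,000 patients (Section 4.4); 95% intervals and a linear mixed model (Section 7). The plan states no event rate, group size or interval width, so it has no figure of its own to reproduce.

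**Assumptions.** Two-sided intervals; splits of 500/500, 300/700, 250/750 and 100/900; rates of 1% to 15% for uncommon events and 20% to 70% for common ones.

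**Formulas**, leaving clustering aside:
- True variance of the difference: p1(1-p1)/n1 + p2(1-p2)/n2.
- Linear-model variance: s² × (1/n1 + 1/n2), with s² = [n1·p1(1-p1) + n2·p2(1-p2)]/N.

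**Worked case: 250 patients at 5%, 750 at 2%.**
- Group variances: 0.05 × 0.95 = 0.0475 and 0.02 × 0.98 = 0.0196.
- True variance: 0.0475/250 + 0.0196/750 = 0.000190 + 0.0000261 = 0.000216; SE 0.0147.
- s² = (250 × 0.0475 + 750 × 0.0196)/1,000 = 0.0266. Model variance: 0.0266 × (1/250 + 1/750) = 0.000142; SE 0.0119.
- Ratio: 0.0119/0.0147 = 0.81. Swapping the rates gives the inverse, 1.24.

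**Exact coverage of the nominal 95% linear-model interval**, by enumerating both binomial distributions (smaller group first):

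| Rates | 250/750 | 300/700 | 100/900 |
|---|---|---|---|
| 3% v 1% | 87.2% | 88.3% | 83.9% |
| 5% v 2% | 88.2% | 89.9% | 81.9% |
| 10% v 3% | 86.5% | 88.6% | 79.0% |
| 15% v 5% | 87.7% | 89.3% | 81.6% |
| 2% v 5% | 98.4% | 97.9% | 99.1% |
| 5% v 15% | 98.6% | 98.1% | 99.5% |

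**Where the error is absent or small.**
- Equal groups: 94.9% to 95.8%.
- Equal rates (1% to 15%) in unequal groups: 94.7% to 96.1%. The linear-model test then rejects 3.9% to 5.3% of the time.
- Common events (20% v 25%, 30% v 40%, 50% v 60%, 60% v 70%, in either or one direction) in unequal groups: 93.4% to 96.3%.

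**Check with clustering.** Linear mixed models were fitted to simulated binary data, assuming 20 hospitals, a hospital SD of 0.5 on the logit scale and 400 replicates per scenario. Coverage was 87.0% (250/750, 5% v 2%), 98.3% (250/750, 2% v 5%), 76.5% (100/900, 10% v 3%) and 99.0% (100/900, 3% v 10%). Monte Carlo error is about 0.5 to 2 points. Many fits put the hospital variance at zero, and failed fits were replaced by an ordinary linear model. The exact results do not depend on this.

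**Would a robust standard error be enough?** Not in sparse cells. The unequal-variance interval covers 93% to 95% at 250/750 for the differing rates above. With both rates at 1% it covers 90.1% at 250/750, where its test rejects 9.9% of the time against 4.3% for the linear model, and 64.1% at 100/900. A hospital-cluster-robust standard error, simulated with 20 hospitals of 50 and a 25% smaller group, covered 92.7% at 5% v 2% and 91.2% at 3% v 1%. The Newcombe score-based interval covers about 95% to 96% throughout, but ignores clustering.

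**The case against.** The case for leaving the plan alone has five parts.

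- **A linear model for proportions is a recognised way to get risk differences directly.** This stands for the estimate. It does not rescue the interval unless the unequal variances are dealt with, and Section 7 does not do so.
- **The significance tests are sound.** A reader might infer that the 0.05 threshold is compromised. That is not supported: a test's level is defined at equal rates, where the two variances are equal and the single-variance model is right. This objection stands in full.
- **The scenarios are chosen, not documented.** This also stands. No sex split, body mass index split, event rate or number of hospitals is given, and the obvious rare events (ECMO, pneumothorax) are collected fields in Section 5.4.3 rather than listed main or secondary parameters. For commoner events the error is at most about 2 points of coverage.
- **Ventilation mode is not left without an estimate.** A reader might infer that a main parameter has no defined comparison. Section 7 already describes categorical variables by counts and proportions, and one risk difference per category is the ordinary reading. The mode categories are not listed either; that there are more than two is only inferred from the separate volume, pressure and pressure-support fields. What remains is a wording clarification.
- **The study is observational and no confirmatory decision depends on these intervals.** This limits the weight of the point but does not make the intervals right.

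**Conclusion.** The point holds in a limited form. Section 7 states a method, and for binary variables that method gives intervals with the wrong coverage when two conditions meet: group sizes are unequal, and the rates of an uncommon event differ substantially. Under the assumed splits of 250/750 or 300/700, coverage is about 87-90% if the smaller group has the higher rate and about 98-99% in reverse. At 100/900 with the higher rate in the smaller group it is about 82-84%, and 79% at 10% v 3%.

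With equal groups, equal rates or common events, coverage is about 93-96% and little is lost. The documents do not show how many of this study's comparisons fall into the affected region. Nothing here supports a claim of an inflated false-positive rate or of a biased risk difference.

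**What to change.** In Section 7, replace the sentence on categorical variables with the following:

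- Obtain risk differences for binary variables from a mixed-effect logistic model with hospital as random effect, by marginal standardisation, with a hospital-level bootstrap or delta-method 95% interval.
- Name a fallback for sparse events and the condition that triggers it, for example a score-based interval such as Newcombe, reported with a note that it ignores clustering.
- Do not rely on robust or cluster-robust standard errors alone where cells are sparse.
- As a clarification, state that ventilation mode and other multi-level variables are reported as one risk difference per level, and list the levels.

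The coverage of the standardised interval was not simulated here. The reason to prefer it is that a logistic model lets the variance follow the rate in each group. The cost is a few sentences, a little more analysis work in R and no new data. The downside is possible non-convergence for very rare events, which the fallback covers.
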